Several field studies have confirmed the important role of zinc in immunity and risk of infection. Controlled trials have demonstrated therapeutic effect of zinc on diarrheal episodes, preventive effects on the incidences of diarrhea and acute lower respiratory tract infections (ALRI), and positive effects on physical growth. Evidence of improvement of cellular immune status with zinc supplementation is also present. These studies suggest that supplementation with zinc may markedly improve the protective immune responses against these infectious diseases thereby reducing the severity and episodes of the diarrhea and ALRI. In humans, iron deficiency is associated with an increased risk of infection and its prevention/ or treatment may be expected to lower the incidence of common infections. Several studies have shown that individuals with iron deficiency show impairment of cell-mediated immunity, humoral immunity and phagocyte microbicidal function. The benefit of micronutrient mixture supplementation is controversial. However, if zinc, iron or micronutrient mixture have positive effect on the immune response, it may be adopted as a public health measure to enhance the efficacy of vaccines. The ongoing study entitled "A community-based, randomized, controlled trial to assess the efficacy of iron and / or zinc or a micronutrient mix supplementation to reduce anemia and morbidity and to improve growth and development in Bangladeshi infants" (Protocol #99-014) is a community based, double blind, randomized, controlled trial to evaluate the efficacy of weekly supplementation of iron and / or zinc or a micronutrient mix for six months in infants beginning 6 months of age. Five groups will be studied. (I) 20 mg iron with 1 mg riboflavin, (ii) 20 mg zinc with 1 mg riboflavin, (iii) both iron and zinc with riboflavin, (iv) a micronutrient mix (UNICEF mix), and (v) riboflavin only (placebo) will be studied. The outcome variables that will be measured are: (a) iron status, (b) zinc status, (c) copper status, (iv) diarrheal morbidity, (v) growth, and (f) cognitive, psychomotor and behavioral development. Eight hundred infants will be selected from the Matlab villages and will be enrolled in the study over a period of six months. The objective of the present protocol is to study the humoral and cell-mediated immune responses in children before and after micronutrient supplementation. The impact of iron and / or zinc supplementation and micronutrient mixture supplementation on the immune status of infants will be studied in the proposed addendum. Infants from selected Matlab villages meeting the inclusion and exclusion criteria as given in the original protocol will be enrolled in the parent study. In addition to the criteria set for the original protocol, subjects who develop any infection including ARI or diarrheal diseases will be excluded from the proposed study since the infection may have an effect on the immune responses of these subjects. Before and 6 months after supplementation, the following will be studied: (1) The levels of total and specific IgA (response against measles/oral Polio vaccine) in serum and secretory IgA in stool. (2) Thymidine uptake assay of lymphocytes after stimulation with mitogens and measurement of IL-2 levels in the culture supernatant to study proliferation responses. (3) Multitest CMI skin test and (4) Phenotypic changes in the peripheral blood mononuclear cells to study the cell-mediated immune response in infants. (5) Complement response (C3, C5) in infants. Long term supplementation of iron and/or zinc or micronutrient mix in infants six months onward will allow us to understand whether any of these supplementation alone or in combination improves humoral immune responses (ie. whether there is an increase in levels of total IgA and complements and specific IgG response against vaccines (measles/oral polio vaccine) in serum and s-IgA in stool), and cellular immune status (CMI, proliferation response).

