Infants from selected Matlab villages meeting the inclusion and exclusion criteria as given in the original protocol will be enrolled in the parent study. In addition to the criteria set for the original protocol, subjects who develop any infection including ARI or diarrheal diseases will be excluded from the proposed study since the infection may have an effect on the immune responses of these subjects.

Outcome Variables and Sample size Determinants

The following outcome variables will be measured:

- | | | |
|------|-------------------------|---|
| (i) | Humoral responses: | IgA in serum
Serum IgG responses to measles/Polio vaccines
sIgA in stool

Complement components C3 and C5 in serum |
| (ii) | Cell mediated immunity: | Proliferative response of peripheral lymphocytes to mitogens
Interleukin 2 in culture supernatant of proliferative lymphocytes
Phenotypic changes in the peripheral blood |

Table 1. Sample size calculations:

Outcome variables	Expected levels in the control group	Expected level in the treatment group (expected % improvement/reduction)	*Sample size required in each group	References
1. IgA in serum, mg/L	81±32	111±26	19	17
2. s-IgA in stool, g/L (for zinc)	0.05±0.01	1.1±0.45	3	36
3. s-IgA in stool, mg/dl (for iron)	0.05±0.01	7.4±0.25	2	27
4. Antibody titers against Polio virus vaccine	169	346	99	33
5. [§] Response to PHA	31±9	58±13	4	17
6. IL-2 in culture supernatant, units/ml	106.5±99	137.3±67	149	28
7. CMI, % of anergic children	67%	47%	131	15
8. Phenotypic changes	0.43±0.53	2.09±1.68	12	28
a) CD3				
b) CD4	0.30±0.39	1.43±1.24	14	28
c) CD8	0.13±0.17	0.76±0.54	9	28

[§]Stimulation index, mean±SD. A loss of follow-up of 20% has been included. *Sample size required in each group of infants supplemented with either zinc alone or iron alone, or zinc and iron in combination or the multimix. Allowance for 10% drop-out has been made. Since sample size is different for each variable, for convenience we decided that for variables 1, 2, 3, 5, and 8, sample size is 20. Sample size for variables 4, 6 and 7 will remain the same as shown in the table.

Methodology

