International travel is required for carrying out flow cytometric assay at the Division of Infectious Diseases, Karolinska Institutet, Sweden.

A community-based, randomized, controlled trial to assess the efficacy of Iron and/or Zinc or a micronutrient mix supplementation to reduce anemia and morbidity and to improve growth and development in Bangladeshi Infants

Abstract summary for the ethical review committee

Diets given to infants in most developing countries are often deficient in multiple micronutrients including iron and zinc. Consequently, many of these infants develop multiple micronutrient deficiencies, particularly iron and zinc deficiency by six months of age. Iron deficiency during early childhood causes anemia and impairs the child's physical and mental development. Recent controlled trials have shown a therapeutic effect of zinc on diarrhoeal episodes, preventive effects on diarrhoea and ALRI morbidities, positive effects on growth, immune function, and child development. Thus, in countries where there is no immediate solution to correct micronutrient deficiencies through dietary approaches, it is important to define the need and feasibility of micronutrient supplementation of infants 6 months onwards to prevent anemia, reduce morbidity, and to improve growth, mental, psychomotor, and behavioural development.

The proposed study is a community-based, prospective, double-blind, randomized, controlled trial to evaluate the efficacy of weekly supplementation of iron and/or zinc or a micronutrient mix for six months in infants beginning 6 months of age. Five groups: i) 20 mg iron with 1 mg riboflavin, ii) 20 mg zinc with 1 mg riboflavin, iii) both iron and zinc with riboflavin, iv) a micronutrient mix, and iv) riboflavin only (placebo) will be studied.

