The following outcome variables will be measured: a) Iron status, b) Zinc status, c) Copper status, d) diarrhoeal morbidity, e) Growth, and f) Cognitive, psychomotor, and behavioural development. Eight hundred infants from selected Matlab villages meeting the eligibility criteria will be enrolled in the study over a six month period: Infants will be stratified by height-for-age z-scores using -2 z-score height-for-age as the cut-off. The infants in each strata will then be randomized to one of the five study groups using a block randomization procedure. Trained CHWs will visit the infants every week to collect morbidity data. The CHWs will feed the infants the assigned supplement during the weekly home visits. To assess growth, weight, length, and MUAC of study children will be measured at enrollment and thereafter every month. Finger prick blood samples will be collected from each study infant at the start and end of the follow-up and will be tested for haemoglobin. About 3 ml venous blood samples will be collected by a trained nurse from 50% of the study infants at the start and end of the follow-up and will be tested for serum transferrin receptor (sTfR), ferritin, zinc, and copper. An assessment of mental, psychomotor, and behavioural developments will be carried out in a 50% sample of study infants at the start and end of the trial (6 months and 12 months) by a trained psychologist using Bailey's Scale of Infant Development, version 2. Dietary data will be collected from a 10% sample of children to assess the dietary intake of zinc, iron and other micronutrients which would help identify any differences in zinc/iron intake in the different treatment groups.

To ensure data quality, the study supervisors and investigators will make spot checks. In addition, a 5% sample of study children will be re-interviewed and re-measured within two days of the original interview/measurement. All questionnaires and data forms will be reviewed by the investigators for accuracy, consistency and completeness. Data will be entered in databases using on-line custom-designed data entry programs. Necessary range and consistency checks will be in-built. Data will be periodically checked by running and reviewing frequency distributions and cross-tabulations.

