3. Sterile non-touch techniques will be used to collect blood samples to reduce the risk of infection.
4. Identity of all study participants will remain confidential. Records will be used by study staff only in connection with carrying out their obligations relating to the clinical trial and every effort

will be made to keep the records as confidential as possible. All data forms will be kept in a locked file cabinet. Data will be analyzed and published using subjects' identification number only without reference to any name or other identity.

5. The mother/caretaker of the study infants will have the study explained to them and will be asked if they agree to participate in the study. Those who agree to participate will be required to sign the consent form. No information regarding potential risk will be withheld.
6. The mothers/ caretakers of study children will be interviewed to collect data on diarrhoea and ARI morbidities in the study infants every week. In addition, dietary data will be collected from a sample of study children once every two months. This interview will not take more than 15 minutes.
7. Children who will receive the supplements are likely to experience fewer episodes of diarrhoea and ARI and improved physical growth and mental development. In addition, if the proposed intervention is proved to be beneficial and incorporated with the existing program, it will significantly improve child health and survival.
8. Matlab-Demographic Surveillance System records will be used to select the study subjects. About 4 ml blood will be collected 2 times from 50% of the study infants.

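### The immune study excludes any infant who develops an infection, with no time window; read plainly, this selects infants after randomisation on something the supplements are expected to change

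*Protocol*

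**What the plan says.** The rule stands in the Protocol under Research Design and Methods, Study Subjects, and again in the Project Summary: "subjects who develop any infection including ARI or diarrheal diseases will be excluded from the proposed study". The reason given is "since the infection may have an effect on the immune responses of these subjects". Neither place says when the infection must occur, how severe it must be, or how it is ascertained.

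The abstract for the ethical review committee describes the design. Infants are "randomized to one of the five study groups using a block randomization procedure", and supplements are given weekly "for six months in infants beginning 6 months of age". It adds that "Trained CHWs will visit the infants every week to collect morbidity data". Item 6 of the strategies to address ethical issues confirms that the weekly interviews cover both diarrhoea and ARI.

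The parent trial's outcome list includes "d) diarrhoeal morbidity, e) Growth". ARI is not on that list, although it is recorded. Item 7 of the same strategies says: "Children who will receive the supplements are likely to experience fewer episodes of diarrhoea and ARI". The Project Summary likewise credits zinc with preventing diarrhoea and acute lower respiratory infection.

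The Background section (Addendum) says that infection causes micronutrient loss and often immunosuppression. It cites cell-mediated immune deficiency as an independent risk factor for diarrhoea.

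**The concern.** An exclusion is harmless to a randomised comparison if it depends only on what is known before treatment starts. This one, read plainly, depends on what happens during six months of treatment. By the protocol's own account, the excluding event is linked to both sides of the comparison:

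- Treatment is expected to make infection less frequent, so fewer infants would be excluded from the supplemented arms than from placebo.
- Poor immune status is expected to make infection more likely, so infants with poor values on the outcomes being measured would be the likelier ones to go.

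The analysed arms could then differ in immune status even if the supplements did nothing to immunity. If the supplements work partly by preventing infection, that part of the effect is removed from view. The rule also takes away infants for whom Table 1 makes no separate allowance.

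**Working it through.** **1. Which analyses are touched.** The Data Analysis section names three.

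- Multiple regression for additive and multiplicative effects compares arms, so it is exposed to the selection directly.
- The chi-square test of responder proportions is exposed in the same way when made between arms.
- The Wilcoxon signed-rank test compares pre with post values within infants. It does not use the randomised contrast, but its result would apply only to infants who stayed infection-free.

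**2. Table 1's loss allowance.** Alpha and power are not stated; I assume two-sided 0.05 and 80%.

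- IL-2: the difference is 137.3 - 106.5 = 30.8 and the pooled SD is sqrt((99² + 67²)/2) = 84.5. Then n = 2 × (1.960 + 0.842)² × 84.5² / 30.8² = 118.2, so 119. With 20% loss, 119/0.8 = 148.75, so 149. The table says 149.
- CMI anergy: 67% against 47% with continuity correction gives 105, and 105/0.8 = 131.25. The table says 131.
- Serum IgA: 15/0.8 = 18.75, so 19. The table says 19.

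These rows therefore carry a 20% allowance and nothing further. (The footnote also mentions 10%; that inconsistency is a separate matter.)

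**3. Share excluded.** The documents give no incidence, so the rate L (infections of any kind per child-year) is an assumption. With a Poisson count over half a year, the infection-free share is exp(-L/2). The next table applies this to Table 1's numbers after 20% loss (131 × 0.8 = 105 for CMI, 149 × 0.8 = 119 for IL-2), taking loss and infection as independent. Power is for Table 1's own effects. The CMI power is computed without continuity correction, so it starts at 84% rather than 80%.

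| L | Excluded | CMI n per arm (power) | IL-2 n per arm (power) |
|---|---|---|---|
| 0 | 0% | 105 (84%) | 119 (80%) |
| 0.5 | 22% | 82 (74%) | 93 (70%) |
| 1 | 39% | 64 (63%) | 72 (59%) |
| 2 | 63% | 39 (43%) | 44 (40%) |
| 4 | 86% | 14 (18%) | 16 (18%) |

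Half the infants are lost at L = 2 × ln 2 = 1.39. The exclusion alone equals the 20% allowance at L = -2 × ln 0.8 = 0.45. Variation in susceptibility between infants would raise the infection-free share somewhat for the same mean rate.

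**4. Differential retention.** Suppose a supplement cuts infections by 20% to 30% (assumption) and L = 2. Placebo retains exp(-1) = 37%. The supplemented arm retains exp(-0.8) = 45% to exp(-0.7) = 50%.

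**5. Bias with no true immune effect.** Two illustrative simulations compared mean immune outcome between infection-free infants of the two arms.

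- Model A: susceptibility log-SD 0.5, correlation of immunity with susceptibility 0.3 to 0.7 in size, infections cut by 25% to 40%, L = 2 to 6. Bias is about -0.03 to -0.19 SD. At L = 4, a 25% cut and correlation 0.5, 20% of placebo and 28% of supplemented infants are retained, and the bias is -0.07 SD.
- Model B: the immune outcome itself lowers the log infection rate by 0.5 per SD. At L = 2 and a 20% to 30% cut, bias is about -0.08 to -0.11 SD.

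If the supplement does not change infection, Model B gives essentially no bias. If infections are halved at L = 4, it gives -0.31 SD, so the quoted range is not a bound. For scale, Table 1's planned IL-2 effect is 30.8/84.5 = 0.36 SD and its serum IgA effect is 30/29.2 = 1.03 SD.

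**The case against.** The best defence is that the sentence is an eligibility criterion. It sits under Study Subjects and is added to the parent trial's entry criteria, which are not shown. The reason given would also fit infection present at a blood draw. This stands to the extent that the timing is not written, and a post-randomisation rule is the natural reading rather than a stated fact. It does not clear the text. Only a rule confined to baseline is harmless, and the text does not confine it. A rule confined to illness at the 12-month draw would still act after randomisation.

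The sponsor also has a genuine reason, since infection can disturb immune measurements. A sensitivity analysis can address that without removing infants from the main comparison.

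Three stronger inferences are tempting, and the documents do not support them:

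- **That the rule removes most of the sample.** No infection rate is given. The dissemination section says only that infants in such settings often have multiple infections. More than half are lost only if L exceeds about 1.39.
- **That the rule explains the shortage of blood samples.** Half of 800 infants over five arms is about 80 per arm, already below the 99 (polio antibody) and 149 (IL-2) in Table 1. That is a separate problem. CMI is a skin test and need not be limited by it.
- **That the rule would manufacture a benefit, or that the bias is known.** In both simulations it runs against the supplement, so it would tend to hide benefit. For outcomes with large planned effects, such as serum IgA, a bias of this size is small. Its sign and size depend on inputs that are not in the documents.

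**Conclusion.** The point stands as a design defect that should be corrected before infants are dropped. Followed as written, the rule selects the immune study's infants on a variable that the protocol ties to both treatment and outcome. That much rests on the wording and on the protocol's own expectations, without any assumed infection rate. The timing is the plain reading and needs to be stated either way.

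The numbers are conditional. The loss is 22% to 86% for an assumed 0.5 to 4 infections per child-year, with no allowance beyond the 20% already in Table 1. The bias of roughly -0.03 to -0.19 SD is illustrative. It matters most for outcomes with modest planned effects, such as IL-2.

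**What to change.** 1. Reword the Project Summary and Study Subjects so that any infection-based exclusion applies only to infection present at or before the baseline sample, before supplementation starts.
2. Take the 12-month sample from all randomised infants in the immune study, whether or not they had an infection, and analyse them in the arm assigned.
3. Use the weekly morbidity records to flag infection near the 12-month sample, with a window fixed in advance, and use that flag in a sensitivity analysis only.

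The cost is a wording change in two places and no new type of data, although more 12-month samples would be collected and assayed than under the exclusion. Recently ill infants may add somewhat to outcome variability. The estimate also becomes the total effect of supplementation, including any part that works through fewer infections; the protocol should say so. The change needs to come early, because an immune sample not taken at 12 months cannot be recovered.

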3. Multitest CMI skin test will be performed to study the cell-mediated immune response in infants.

4. To study phenotypic changes in the peripheral blood mononuclear cells.
5. To study the complement response (C3, C5) in infants.

Background of the Project including Preliminary Observations

Describe the relevant background of the proposed study. Discuss the previous related works on the subject by citing specific references. Describe logically how the present hypothesis is supported by the relevant background observations including any preliminary results that may be available. Critically analyze available knowledge in the field of the proposed study and discuss the questions and gaps in the knowledge that need to be fulfilled to achieve the proposed goals. Provide scientific validity of the hypothesis on the basis of background information. If there is no sufficient information on the subject, indicate the need to develop new knowledge. Also include the **significance and rationale** of the proposed work by specifically discussing how these accomplishments will bring benefit to human health in relation to biomedical, social, and environmental perspectives. (DO NOT EXCEED 5 PAGES, USE CONTINUATION SHEETS).

Original protocol:

The above study (entitled "A community-based, randomized, controlled trial to assess the efficacy of iron and / or zinc or a micronutrient mix supplementation to reduce anemia and morbidity and to improve growth and development in Bangladeshi infants") (Protocol #99-014) is a community based, double blind, randomized, controlled trial to evaluate the efficacy of weekly supplementation of iron and / or zinc or a micronutrient mix for six months in infants beginning 6 months of age. Five groups will be studied. (i) 20 mg iron with 1 mg riboflavin, (ii) 20 mg zinc with 1 mg riboflavin, (iii) both iron and zinc with riboflavin, (iv) a micronutrient mix (UNICEF mix), and (v) riboflavin only (placebo) will be studied.

The outcome variables that will be measured are: (a) iron status, (b) zinc status, (c) copper status, (iv) diarrheal morbidity, (v) growth, and (f) cognitive, psychomotor and behavioural development. Eight hundred infants will be selected from the Matlab villages and will be enrolled in the study over a period of six months. Selection criteria are described in the original

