Immunological assays including enzyme linked immunosorbant assays (ELISA), lymphocyte proliferation assay, will be carried out at ICDDR,B since the techniques have been standardized and the equipment needed for carrying out the assays are available in ICDDR,B. However, to perform sterile work, a biohazard hood will be required at Matlab. For separating lymphocytes from blood, a refrigerated table-top-centrifuge will also be needed at Matlab. An ultra low freezer (-80° C) will be required to store lymphocytes after separation from whole blood. These lymphocytes will be phenotyped later by flow cytometry. Since fluorescent associated cell sorter (FACS) is not available at ICDDR,B, frozen cells have to be carried in dry ice (-70° C) to Sweden. FACS will be available to the PI to perform flow cytometric assay (phenotyping) at the Division of Infectious Diseases, Karolinska Institutet, Sweden.

Data Analysis

Describe plans for data analysis. Indicate whether data will be analyzed by the investigators themselves or by other professionals. Specify what statistical softwares packages will be used and if the study is blinded, when the code will be opened. For clinical trials, indicate if interim data analysis will be required to monitor further progress of the study. (TYPE WITHIN THE PROVIDED SPACE).

Baseline characteristics of the different supplementation/treatment and comparison groups will be examined for group comparability as described in the original protocol.

To examine the effect of individual micronutrient i.e. zinc or iron on the immune parameters between the pre and post supplementation days, Wilcoxon-signed Rank test will be used. To examine the proportion of subjects responding to a particular supplement, Chi-square test will be performed. To examine the potential additive and multiplicative effects of providing zinc, iron and other micronutrients on the immune parameters, multiple regression analyses will be performed.

Ethical Assurance for Protection of Human Rights

Describe in the space provided the justifications for conducting this research in human subjects. If the study needs observations on sick individuals, provide sufficient reasons for using them. Indicate how subject's rights are protected and if there is any benefit or risk to each subject of the study.

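### Table 1 gives two-group, control-versus-treatment sizes, but its footnote assigns them only to the four supplemented groups and leaves the riboflavin-only control without a number for any immune outcome

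*Protocol*

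**What the plan says.** The Background section lists five randomized groups, the last two being "iv) a micronutrient mix (UNICEF mix), and (v) riboflavin only (placebo) will be studied".

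Table 1, under Outcome Variables and Sample size Determinants, has one column headed "Expected levels in the control group" and another headed "Expected level in the treatment group (expected % improvement/reduction". Its size column carries an asterisk, and the asterisked note reads "Sample size required in each group of infants supplemented with either zinc alone or iron alone, or zinc and iron in combination or the multimix". The same note fixes 20 per group for variables 1, 2, 3, 5 and 8, and keeps the printed sizes for variable 4 (polio titre, 99), variable 6 (IL-2, 149) and variable 7 (skin-test anergy, 131). On losses it says "A loss of follow-up of 20% has been included" and then also mentions a 10% drop-out allowance.

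The Data Analysis section plans a Wilcoxon signed-rank test of before against after, a chi-square test on the proportion responding, and a regression: "To examine the potential additive and multiplicative effects of providing zinc, iron and other micronutrients on the immune parameters, multiple regression analyses will be performed".

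**The concern.** A size from a control-versus-treatment calculation holds only if the control group is also that large. The footnote names the groups that receive the size, and the control is not among them. Several outcomes are to be measured in only 20 infants per group, so the number assigned to each group matters in practice. Someone planning assays from the footnote alone would find no riboflavin-only quota.

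The first listed analysis would not expose the gap, because a signed-rank test works within one group and needs no control. Yet a before-to-after change between 6 and 12 months cannot be credited to a supplement without concurrent controls. The Background itself notes that measles vaccine is given at 9 months, so measles antibody may be expected to change in any arm. The randomized comparison with riboflavin only, and the zinc-by-iron interaction, both depend on having enough riboflavin-only infants.

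**Working it through.** **Inputs.** Means, SDs, proportions and printed sizes come from Table 1. Enrolment of 800 infants in five arms and venous blood from 50% of them come from the Background and the abstract for the ethical review committee. Alpha and power are not stated. Two-sided 5% and 80% are inferred because they reproduce the table.

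**Step 1: reproduce Table 1.** For means, n per group = (1.960 + 0.842)² × (SD₁² + SD₂²) / (difference)², rounded up, divided by 0.8 for the 20% loss, and rounded up again.

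| Row | n before rounding | rounded up | ÷ 0.8 | printed |
|---|---|---|---|---|
| Serum IgA (81±32, 111±26) | 14.83 | 15 | 18.75 | 19 |
| s-IgA, zinc (0.05±0.01, 1.1±0.45) | 1.44 | 2 | 2.5 | 3 |
| s-IgA, iron (0.05±0.01, 7.4±0.25) | 0.01 | 1 | 1.25 | 2 |
| PHA (31±9, 58±13) | 2.69 | 3 | 3.75 | 4 |
| IL-2 (106.5±99, 137.3±67) | 118.23 | 119 | 148.75 | 149 |
| CD3 (0.43±0.53, 2.09±1.68) | 8.84 | 9 | 11.25 | 12 |
| CD4 (0.30±0.39, 1.43±1.24) | 10.39 | 11 | 13.75 | 14 |
| CD8 (0.13±0.17, 0.76±0.54) | 6.34 | 7 | 8.75 | 9 |

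For IL-2, for example: 7.849 × (9801 + 4489) / 30.8² = 118.2.

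For "CMI, % of anergic children" (67% against 47%), the two-proportion formula with continuity correction gives 105, and 105 / 0.8 = 131.25 against the printed 131. This row fits if the last step is rounded to the nearest integer. The polio-titre row has no SD and cannot be checked.

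A one-sample calculation does not fit: IL-2 would need about 81 and anergy about 45 before losses. A 10% allowance does not fit either (IL-2 118.2 / 0.9 = 131.4). The printed sizes are two-group sizes with equal arms.

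**Step 2: what the control group needs.** The same number as each supplemented group.

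| Outcome | per group | four groups | five groups |
|---|---|---|---|
| Variables 1, 2, 3, 5, 8 (each) | 20 | 80 | 100 |
| 4, polio titre | 99 | 396 | 495 |
| 6, IL-2 | 149 | 596 | 745 |
| 7, skin test | 131 | 524 | 655 |

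**Step 3: power when the control group is smaller.** IL-2, 149 treated, before losses: power = Φ(30.8 / √(99²/n_c + 67²/149) − 1.96).

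- n_c = 80: 30.8 / √(122.5 + 30.1) = 2.49; power about 70%
- n_c = 40: 30.8 / √(245.0 + 30.1) = 1.86; power about 46%
- n_c = 20: 30.8 / √(490.1 + 30.1) = 1.35; power about 27%

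**Step 4: the regression if no control were assayed.** The abstract for the ethical review committee codes the parent trial's regression with indicators for zinc and for iron and their interaction. With only the cells (zinc, iron) = (1,0), (0,1) and (1,1), an intercept, two main effects and an interaction make four parameters on three cells: rank 3. Giving the multimix its own term adds one cell and one parameter and changes nothing. The two main effects could then be obtained only by assuming the interaction is zero.

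**Step 5: who is bled.** 50% of 800 is 400, and 400 / 5 = 80 per arm if allocation is equal (an assumption). That covers 20 per arm. It is below 99 and 149 in every arm, supplemented or not. IL-2 power with 80 against 80, before losses: 30.8 / √(14290/80) − 1.96 = 0.34, or about 63%.

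**The case against.** The column heading speaks of each group, beside columns for both control and treatment. The footnote can be read as saying only which supplements the treatment group may stand for, one size serving all four contrasts. On that reading the riboflavin-only group is covered and the omission is loose drafting. This may well be what was meant, but the note that defines the groups lists four by name, and no other section supplies the fifth number.

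A reader might go further and infer that no placebo samples will be taken or assayed. The documents do not support that. The riboflavin-only arm is one of the five to be studied. Methodology describes blood and stool collection without restricting it to any arm, and the 50% blood draw excludes none. Data Analysis compares baseline with comparison groups, and the zinc and iron indicators presuppose infants with neither. The loss of the interaction and of any concurrent control is therefore conditional on a literal reading of the footnote.

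A reader might also infer that rewording the footnote restores the Table 1 power in every row at no further cost. It does not. For variables 4 and 6 about 80 bled infants per arm is too few whatever the footnote says. Variable 7 is a skin test that the parent blood draw does not cover.

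**Conclusion.** The point stands as an inconsistency between a sizing rule and the calculation it annotates. Table 1 rests on control groups as large as the treated groups, and the footnote gives the control no number. This is more than detail that could be left to an analysis plan, because the protocol does fix group sizes and fixes them for four groups out of five.

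The size of the effect depends on how many riboflavin-only infants are assayed, which is unstated. For IL-2 it runs from about 70% power with 80 controls to 27% with 20 (149 treated, before losses), and to no controlled comparison with none. For the outcomes sized at 20, an equal control group is enough: 20 × 0.8 = 16 remain after a 20% loss, against at most 15 needed (serum IgA).

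The conclusion assumes two-sided 5% alpha and 80% power (inferred), the 20% loss allowance (the only one of the two stated that reproduces the table) and equal allocation for the figure of 80 per arm. The polio-titre row is taken as printed.

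**What to change.** Reword the Table 1 footnote so that the size is the one required in each of the five groups, including the riboflavin-only group, and give five-group totals.

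- **Variables 1, 2, 3, 5 and 8:** 20 riboflavin-only infants, 100 in total per outcome. The cost is one sentence and assays for one more group, in infants whom the 50% blood draw does not exclude.
- **Variables 4 and 6:** make the riboflavin-only group no smaller than any supplemented group, and restate the achievable number and its power. At about 80 per arm the printed 99 and 149 are out of reach. Reaching them would mean bleeding more than 50% of infants, which is a larger change than a footnote.
- **Variable 7:** state that the riboflavin-only group is skin-tested at the same number as the other groups (131 as printed, 655 in total). This is extra fieldwork, because the parent blood draw does not include it.
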